13. SAMPLE SIZE

The sample size has been calculated based on the main outcome of the study, i.e. the mean change vs baseline of the global score of The National Eye Institute 25-Item Visual Function Questionnaire (VFQ-25) in patients with moderate-stage glaucoma (*Ophthalmol 2015 Nov Acta 19*).

When the sample size in each sequence group is 100, (a total sample size of 200) a 2 x 2 crossover design will have 80% power to detect a difference in means of 3.0 (the difference between study treatment mean, μ_1 , of 3.0 and placebo mean, μ_2 , of 0) assuming that the crossover ANOVA \sqrt{MSE} is 10.607 (the standard deviation of differences, σ_d , is 15.0) using a two group t-test (crossover ANOVA) with a 0.05 two-sided significance level.

The total sample size is adjusted to 220 patients considering an expected dropout rate of about 10%.

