4. SCHEDULE OF ASSESSMENTS

	Screening / Baseline (beginning of 1 st period)	3-month Visit (end of 1 st period, beginning of 2 nd period)	6-month Visit	9-month Visit (end of 2 nd period)
Informed consent	X			
Inclusion/exclusion criteria	X			
Complete ophthalmological examination*	X	X	X	X
Randomization to study sequence	X			
VFQ-25	X	X	X	X
SF-36	X	X	X	X
Dispensing treatment	X	X	X	
Concomitant medications	X	X	X	X
Adverse events		X	X	X

*Including visual acuity (VA), VF (24-2, SITA standard strategy), fundus assessment, biomicroscopy (with specific lens evaluation using Lens Opacities Classification System III (LOCS III) criteria), IOP assessment. Gonioscopy and optic nerve head (ONH) topography parameters measured by optical coherence tomography (OCT) are required at screening to verify inclusion/exclusion criteria.

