7. STUDY OUTCOMES

The primary outcome will be the mean change of “intra-patient” global score of the VFQ-25 questionnaire after Neurotidine[®] vs placebo at 6 months compared to baseline. Other outcomes include the change of other scores (e.g. general health, general vision, near and far activities, social, mental, role difficulties, etc.) of two study questionnaires, VFQ-25 and SF-36, as well as the safety and tolerability of citicoline oral solution.

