14. STATISTICAL ANALYSIS

Continuous data will be summarized with standard descriptive statistics (i.e. the mean, standard deviation, minimum, median and maximum, 95% confidence limits). Categorical data will be summarized by frequencies and percentages.

No statistical test will be performed for between-group differences in demographic and baseline features (medical history and efficacy data).

Medical history and adverse events will be described according to System Organ Classes (SOC) and Preferred Terms (PT) using the Medical Dictionary for Regulatory Activities (MedDRA) and will be presented by treatment group.

Previous/concomitant medications will be presented by treatment group using the World Health Organization Drug Dictionary (WHO-DD).

[figure not shown]
The primary efficacy variable will be analysed using crossover ANOVA, considering sequence, subjects, period and treatment as sources of variation.

All study centers will fill in a web-based e-CRF. The Data Center will check the e-CRF and solve all the queries. The Coordinating Center will do the statistical analysis of collected data.

The association between quality of life and measures of visual symptoms, of the ability to perform vision-related activities and clinical findings will be analysed by means of linear regression models.

All analysis will be performed using SAS version 9.4.

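### The month-0 VFQ-25 cancels out of the planned crossover ANOVA, so the primary treatment comparison gains no precision from it; adding it by period could do so at almost no cost

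*Combined protocol and SAP*

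**What the plan says.** Section 7 defines the primary outcome as an intra-patient change in the VFQ-25 global score after Neurotidine "vs placebo at 6 months compared to baseline"; Section 3 has the same definition. Section 13 sizes the trial on "the mean change vs baseline of the global score of The National Eye Institute 25-Item Visual Function Questionnaire (VFQ-25").

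In the Section 4 schedule one column carries the word baseline: "Screening / Baseline (beginning of 1 st period"). The next column is headed "3-month Visit (end of 1 st period, beginning of 2 nd period"), and VFQ-25 is taken there too. Section 10 likewise gives the name of baseline visit to month 0 alone.

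Section 14 specifies the primary analysis as a crossover ANOVA "considering sequence, subjects, period and treatment as sources of variation". No baseline covariate is listed, and the text does not say whether subjects are fixed or random.

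**The concern.** A change-from-baseline outcome looks as if it uses the baseline to sharpen the comparison. In a crossover analysis with a term for subjects it does not, because each patient already serves as their own control and a constant taken from both period scores disappears. The trial collects VFQ-25 before any treatment from every patient, and the primary model as listed draws no precision from it.

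What is at stake is efficiency, not validity. If month-0 scores correlate more strongly with the first-period score than with the later second-period score, they predict part of the within-patient period difference. An analysis that ignores this has a larger standard error than it needs.

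**Working it through.** **Inputs from Section 13:** 100 patients per sequence, difference 3.0, standard deviation of within-patient differences 15.0, √MSE 10.607, two-sided 0.05.

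**1. The plan's own figure.**
- √MSE = 15/√2 = 10.607, as stated.
- The treatment estimate is half the difference between sequences in the mean period difference. Its SE is (15/2) × √(2/100) = 1.061.
- Noncentrality is 3.0/1.061 = 2.83. The noncentral t with 198 degrees of freedom gives power 0.804 (normal approximation 0.807). The stated 80% reproduces.

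**2. Cancellation.** Let B be the month-0 score and Y1, Y2 the two period scores.
- (Y1 − B) − (Y2 − B) = Y1 − Y2.
- On one simulated complete data set, raw scores and changes from month 0 both gave an estimate of 3.716 and an SE of 1.116.
- Limits of this result:
  - With random subjects and about 10% of second periods missing, the two responses gave 3.32 (raw) and 3.63 (change). With fixed subjects both gave 3.389.
  - The between-patient sequence test does depend on the baseline: p = 0.43 raw and 0.08 for change in the complete data set. So do the descriptive mean changes.

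**3. What adjustment could gain.** Regress the period difference on sequence and B. With equal variances at all visits, the share of its variance explained by B is

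R² = (r09 − r03)² / [2(1 − r39)],

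where r03, r09 and r39 are the correlations between months 0 and 3, 0 and 9, and 3 and 9. The documents give none of these, so every value below is an assumption.

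- Equal correlations: the numerator is 0, so R² = 0.
- First-order decay of 0.8 per three-month visit, month-9 endpoint: (0.512 − 0.8)² / [2(1 − 0.64)] = 0.0829/0.72 = 0.115.
- Decay of 0.7: (0.343 − 0.7)² / [2(1 − 0.49)] = 0.1274/1.02 = 0.125.
- Mixed structure, with a share a of the variance stable and the rest decaying: r03 − r09 and 1 − r39 both shrink by (1 − a), so R² is (1 − a) times the decay value. With a = 1/2 it is about 0.06; with a = 5/6 it is about 0.02.
- Month-6 endpoint, with r06 and r36 in place of r09 and r39: decay 0.8 gives 0.16²/0.4 = 0.064, and decay 0.7 gives 0.21²/0.6 = 0.074.

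**4. Translation to power.** The SE becomes 1.061 × √(1 − R²), and the equivalent unadjusted size is 200/(1 − R²).

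| R² | SE | Power | Equivalent patients |
|---|---|---|---|
| 0 | 1.061 | 80% | 200 |
| 0.02 | 1.050 | 81% | 204 |
| 0.06 | 1.028 | 83% | 213 |
| 0.125 | 0.992 | 85% | 229 |

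**5. If month 3 were used as the second-period baseline** (not the natural reading). Section 13 sets "the difference between study treatment mean" and the placebo mean by values of 3.0 and 0.
- Neurotidine-first patients contribute 3 − (0 − 3) = 6 and placebo-first patients contribute 3 − 0 = 3. The mean is 4.5.
- With residual carry-over L in the placebo period after Neurotidine, the estimate is 4.5 − L/2, against 3 − L/2 with month 0 as sole baseline.
- The within-patient contrast is 2Y1 − B − Y2. With equal correlations its SD is √(6 × 112.5) = 25.98 instead of 15, a factor of √3 = 1.73, and power is about 68%.
- A true zero effect without carry-over still reads as zero.

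**The case against.** The strongest reply is that nothing is wrong with the plan as written. The test is valid, the sample size reproduces, and replacing change by score as the response alters no primary result when pairs are complete or subjects are fixed. All of that stands. A covariate is an optional gain, and under equal correlations the gain is nil. That stands too, which is why the range starts at 80% power and 200 patients.

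A reader might go further and infer that the trial would report 4.5 for a true 3.0, because month 3 is called the beginning of the second period, VFQ-25 is taken then, and no sentence rules it out as a baseline. The documents do not support this. Sections 4 and 10 call only month 0 baseline. The outcome definitions name no period-specific baseline. The placebo mean of 0 in Section 13 fits month 0: with month 3 as baseline and no carry-over, the Neurotidine-first patients would have a placebo change of 0 − 3 = −3. Silence in the text is also weak evidence here, since a figure in Section 14 and any content under the Section 15 heading could not be read.

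A reader might also infer that the baseline plays no part anywhere in the analysis. That is too broad, given the limits set out in step 2 of the working.

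**Conclusion.** The point holds as a missed efficiency. With month 0 as the common baseline, and with fixed subjects or complete pairs, the planned model draws no precision from month-0 VFQ-25 for the treatment comparison. Adjustment by period would explain 0% of the variance of the within-patient difference under equal correlations, about 2-6% under mixed structures, and up to about 12% under first-order decay with a month-9 endpoint (6-7% with month 6). Power would be 80-85%, equivalent to 200-229 patients. These figures rest on assumed correlations and equal variances across visits.

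The planned analysis is not invalid and the stated sample size is not wrong on this account. The undefined second-period baseline is a matter of missing detail and does not show that the effect will be overstated.

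**What to change.** In Section 14, add month-0 VFQ-25 by period to the primary model. Equivalently, regress each patient's period difference on sequence and month-0 score. The by-period term is the part that matters: with fixed subjects, a month-0 main effect alone is absorbed by the subjects term. With separate month-0 slopes for each period, raw score and change also give the same treatment estimate if subjects are random, because subtracting B lowers each slope by one and changes nothing else.

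As a secondary clarification, state in Sections 3, 7 and 14 that month 0 is the sole baseline and that the month-3 score does not serve as one.

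The cost is a sentence or two in each section and about one residual degree of freedom (198 to 197 in the period-difference form), more if months 3, 6 and 9 are modelled by visit. No new data or visits are needed. The change should be made before unmasking.

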14. STATISTICAL ANALYSIS

Continuous data will be summarized with standard descriptive statistics (i.e. the mean, standard deviation, minimum, median and maximum, 95% confidence limits). Categorical data will be summarized by frequencies and percentages.

No statistical test will be performed for between-group differences in demographic and baseline features (medical history and efficacy data).

Medical history and adverse events will be described according to System Organ Classes (SOC) and Preferred Terms (PT) using the Medical Dictionary for Regulatory Activities (MedDRA) and will be presented by treatment group.

Previous/concomitant medications will be presented by treatment group using the World Health Organization Drug Dictionary (WHO-DD).

[figure not shown]
The primary efficacy variable will be analysed using crossover ANOVA, considering sequence, subjects, period and treatment as sources of variation.

All study centers will fill in a web-based e-CRF. The Data Center will check the e-CRF and solve all the queries. The Coordinating Center will do the statistical analysis of collected data.

The association between quality of life and measures of visual symptoms, of the ability to perform vision-related activities and clinical findings will be analysed by means of linear regression models.

All analysis will be performed using SAS version 9.4.

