10. DESIGN

The trial will be a randomized, double-masked, placebo-controlled, cross-over study. Eligibility criteria will be assessed, and study procedures clearly explained when the potentially eligible patients are initially visited. If the patients accept to participate in the trial, they will have to sign the informed consent form. After this, the patients will be randomized in a 1:1 ratio to one of the two sequences of the cross-over design: Neurotidine[®]-placebo or placebo-Neurotidine[®]. The randomization will be stratified by centre.

- Baseline visit (beginning of 1st period): Enrolled patients will undergo a complete ophthalmologic examination with VA, VF (24-2, SITA standard strategy), fundus assessment, biomicroscopy (with specific lens evaluation using Lens Opacities Classification System III (LOCS III) criteria), IOP assessment. A masked to treatment evaluator will administer the two study questionnaires (VFQ-25 and SF-36). The patients will be given the bottles for the first 3-month period.
- 3-month visit (end of the 1st period and beginning of 2st period): Patients will undergo a complete ophthalmologic examination with VA, VF (24-2, SITA standard strategy),

biomicroscopy, IOP assessment. Patients will be asked about treatment side effects and all complains/considerations will be recorded. The two study questionnaires (VFQ-25 and SF-36) will be administered. The patients will be given the bottles for the second 3-month period.

- 6-month visit: Patients will undergo a complete ophthalmologic examination with VA, VF (24-2, SITA standard strategy), biomicroscopy, IOP assessment. Patients will be asked about treatment side effects and all complains/considerations will be recorded. Patients will be again administered the 2 study questionnaires (SF-36 and VFQ-25). The patients will be given the bottles for the third 3-month phase.
- 9-month visit (end of the 2st period): Patients will undergo a complete ophthalmologic examination with VA, VF (24-2, SITA standard strategy), biomicroscopy, IOP assessment. Patients will be asked about treatment side effects and all complains/considerations will be recorded. Patients will be administered the two study questionnaires (VFQ-25 and SF-36).

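### Would the planned linear regressions of quality of life on clinical findings mishandle the four repeated visits per patient?

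*Combined protocol and SAP*

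**What the plan says.** Section 14 describes the analysis in one sentence. It opens "The association between quality of life and measures of visual symptoms, of the ability to perform vision-related activities" and closes "clinical findings will be analysed by means of linear regression models". It names no visit, eye, quality-of-life score, patient term or covariance structure.

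The preceding efficacy statement in the same section is more explicit: "The primary efficacy variable will be analysed using crossover ANOVA, considering sequence, subjects, period and treatment as sources of variation".

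The schedule in section 4 places VFQ-25, SF-36 and the row "Complete ophthalmological examination" at baseline, 3, 6 and 9 months, and section 10 (Design) agrees; for the last visit it says "Patients will be administered the two study questionnaires (VFQ-25 and SF-36"). Not every clinical finding is repeated. The footnote to the schedule says that gonioscopy and optic nerve head parameters "measured by optical coherence tomography (OCT) are required at screening to verify inclusion/exclusion criteria", and no later visit requires them.

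Section 7 (Study Outcomes) does not list the association analysis. Section 13 (Sample Size) rests on the VFQ-25 treatment comparison alone.

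**The concern.** Standard linear regression treats every row as independent. A programmer who stacked all visits would enter 800 rows from 200 patients, and rows from one patient resemble each other. Standard errors would then be too small and associations would be declared significant too often. Using baseline alone avoids this but leaves 600 of the 800 rows unused. The patient term named for the primary variable and absent here makes the omission look like an oversight.

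A second worry concerns the variables. The schedule contains no instrument devoted to visual symptoms or vision-related activities. Section 7 names general vision and near and far activities among the questionnaire scores. If quality of life meant the VFQ-25 global score and the predictors were VFQ-25 subscales, a total would be regressed on its own parts and some association would be built in.

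At stake are the confidence intervals and p-values of these association results. The treatment comparison and the safety results are not affected.

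**Working it through.** **The plan's own figure.** No figure is stated for the association analysis. The only one nearby is the power in section 13: "When the sample size in each sequence group is 100, (a total sample size of 200"), difference 3.0, standard deviation of differences 15.0, two-sided 0.05.

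- Root MSE = 15.0/√2 = 10.607, as stated.
- The sequence groups are compared on half-differences with standard deviation 15.0/2 = 7.5. The standard error is 7.5 × √(2/100) = 1.061, and 3.0/1.061 = 2.83.
- Power is 80.7% by the normal approximation and 80.4% by the noncentral t with 198 degrees of freedom. The stated 80% is reproduced and does not depend on the association analysis.

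**If all visits were pooled with no patient term.** Let m = 4 visits, and let ICC_x and ICC_y be the share of variance lying between patients for the predictor and for the outcome. With equally correlated visits:

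- variance inflation D = 1 + (m − 1) × ICC_x × ICC_y
- shortfall in the standard error = 1 − 1/√D
- true two-sided error = 2 × (1 − Φ(1.96/√D))

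The documents give no ICC, so the values below are assumptions.

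| ICC_x, ICC_y | D | Standard error too small by | True error of a 5% test |
|---|---|---|---|
| either one 0 | 1.00 | 0% | 5.0% |
| 0.5, 0.5 | 1.75 | 24% | 13.8% |
| 0.7, 0.7 | 2.47 | 36% | 21.2% |
| 0.9, 0.9 | 3.43 | 46% | 29.0% |
| 1, 1 (ceiling) | 4.00 | 50% | 32.7% |

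For a predictor that is constant within a patient (ICC_x = 1), D = 1 + 3 × ICC_y. With ICC_y from 0.5 to 0.9, D is 2.5 to 3.7, the shortfall 37% to 48% and the true error 21% to 31%. These larger figures apply only if a fixed value is copied onto all four visits. OCT and gonioscopy are the natural candidates, but a value required only at screening pairs most directly with the baseline questionnaire, which gives one row per patient.

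The only related figure in the documents is the root MSE. Its square is 112.5, so the VFQ-25 ICC would be 1 − 112.5/15² = 0.50 for a total standard deviation of 15, and 1 − 112.5/20² = 0.72 for 20. Both total standard deviations are assumptions.

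**If one visit is used, or errors are clustered by patient.** A simulation of 200 patients at four visits with no true association (4,000 runs per setting) gave these rejection rates at ICCs of 0.5, 0.7 and 0.9:

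- pooled, no patient term: 13.2%, 20.7%, 29.2%
- one visit: 4.2%, 4.8%, 5.2%
- pooled, patient-clustered errors: 4.9%, 5.4%, 5.6%

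The last two hold the nominal 5% closely, and both are linear regressions.

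**What a baseline-only fit gives up.** It uses 200 of 800 rows. Relative to a pooled fit with correct errors, its share of the information is D/4.

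- ICCs 0.5: 1.75/4 = 0.44, a loss of 56%.
- ICCs 0.7: 2.47/4 = 0.62, a loss of 38%.
- ICCs 0.9: 3.43/4 = 0.86, a loss of 14%.

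The loss equals the 75% row count against a mixed model with equal ICCs and equal slopes between and within patients.

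**Circularity.** It arises only if the VFQ-25 global score is the outcome and VFQ-25 subscales are the predictors. Section 14 says neither. SF-36 is collected at every visit and is available as the quality-of-life measure.

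**The case for a change.** The strongest case for a change is that the sentence permits the bad analysis, that the authors thought of the patient term for the primary variable but not here, and that the repair is one line of text with no new data. With bilateral disease required by section 8.1, the eye is open too. Leaving outcome and predictors unnamed also allows choices to be made after the data are seen.

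Much of this stands. The sentence is thin, and naive pooling would be a real error under plausible correlations. But the sentence does not prescribe pooling. Authors who model patients explicitly one statement earlier can be expected to recognise the same structure here. Ordinary practice fills each gap: one row per patient or clustered errors, one eye per patient (eligibility already refers to the better eye), and no total regressed on its own parts.

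Nor is the obvious replacement clearly better. A random-intercept model over all visits, with the predictor entered as it stands, yields one slope that mixes differences between patients with changes within a patient. A baseline fit answers a narrower question, but that question is clear and untouched by study treatment. Precision is traded against clarity of target.

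**Conclusion.** The concern does not call for a change. It holds only for one unstated reading, in which all visits are pooled with no patient term. On that reading, standard errors would be 24% to 46% too small and the true error about 14% to 29%, for assumed ICCs of 0.5 to 0.9 in both variables and equally correlated visits. The shortfall cannot exceed 50%, and it vanishes if either ICC is near zero. On the other readings the error rate is correct, and the price of a single visit is precision: 14% to 56% of the information against a correctly analysed pooled fit over the same ICC range.

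What remains is missing detail in a descriptive analysis outside the listed outcomes and the sample size. An analyst can supply it soundly from the data already scheduled. The primary comparison and its 80% power do not depend on it.

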15. EXPERIMENTAL DESIGN

16. REGULATORY, EHTICAL AND STUDY OVERSIGHT CONSIDERATIONS

16.1 Informed consent procedures and documentation

Consent forms describing in detail the study intervention, study procedures and risks are given to the participant and written documentation of informed consent is required prior to starting intervention/administering study intervention.

Informed consent is a process that is initiated prior to the individual’s agreeing to participate in the study and continues throughout the individual’s study participation. Consent forms will

be approved by the IRB/IEC and the participant will be asked to read and review the document. The investigator will explain the research study to the participant and answer any questions that may arise. A verbal explanation will be provided in terms suited to the participant's comprehension of the purposes, procedures, and potential risks of the study and of their rights as research participants. Participants will have the opportunity to carefully review the written consent form and ask questions prior to signing. The participants should have the opportunity to discuss the study with their family or surrogates and think about it prior to agreeing to participate. The participant will sign the informed consent document prior to any procedures being done specifically for the study. Participants must be informed that participation is voluntary and that they may withdraw from the study at any time, without prejudice. A copy of the informed consent document will be given to the participants for their records. The informed consent process will be conducted and documented in the source document (including the date), and the form signed before the participant undergoes any study-specific procedures. The rights and welfare of the participants will be protected by emphasizing to them that the quality of their medical care will not be adversely affected if they decline to participate in this study.

